3.3.2 Independent Anaphylaxis Adjudication Committee

[figure not shown]
An independent Anaphylaxis Adjudication Committee (iAAC) reviews AEs or groups of AEs that are identified as potential cases of anaphylactic, anaphylactoid, or hypersensitivity reactions. Members of the iAAC are external to the Sponsor and review blinded data to adjudicate cases as anaphylaxis per Sampson's criteria (see [Appendix 7; Sampson et al. 2006](#)).

A detailed description of the procedures and data flow of the AAC is maintained in a separate AAC Charter.

3.3.3 Internal Monitoring Committee

[REDACTED]

[REDACTED]

Details with regard to the IMC were documented in an IMC agreement.

4. STATISTICAL METHODS

Cohort A and Cohort B are two independent studies under the same protocol; patients were enrolled with the same entry criteria. The effect of lebrikizumab in the treatment of IPF was assessed as a monotherapy in Cohort A and in combination with pirfenidone in Cohort B. Cohort B was initiated after the completion of the enrollment in Cohort A; Cohort A patients are not allowed to enter Cohort B. Analyses will be performed for each study separately.

The primary analysis will be performed after the completion of the 52-week randomized placebo-controlled period. Analyses will include all assessments up to Week 52.

Descriptive summaries will include mean, standard deviation, median and range for continuous variables, and counts and percentages for categorical variables.

All analyses will be performed using SAS software (Version 9.2 or higher).

4.1 ANALYSIS POPULATIONS

4.1.1 Intent-to-Treat Population

The intent-to-treat (ITT) population will be comprised of all patients who were randomized in the study. All efficacy analyses will be performed on this population with patients grouped according to the treatment assignment at randomization.

4.1.2 Per Protocol Population

A per-protocol population is not deemed necessary for this study and is not defined. However, ongoing monitoring throughout the study course will track the number of patients who violate protocol-defined eligibility or study conduct criteria.

4.1.3 Pharmacokinetic-Evaluable Population

The PK-evaluable population will include all patients who have received at least one dose of study drug, and have at least one non-missing PK observation. Data from these patients will be included in PK analyses, as appropriate, depending on the available time points.

4.1.4 Safety Population

Safety analyses will be based on all patients who received at least one dose of study drug, with patients grouped according to the actual treatment received.

4.2 ANALYSIS OF STUDY CONDUCT

For each cohort, the number of patients randomized will be tabulated by study site and treatment arm. Patient disposition (the number of patients treated and completing each study period) will be tabulated by treatment arm. Premature treatment discontinuation and study discontinuation, as well as reasons for discontinuations, will be summarized.

Eligibility criteria deviations and other major protocol deviations will be summarized.

4.3 ANALYSIS OF TREATMENT GROUP COMPARABILITY

Demographic and baseline characteristics such as age, gender, race, ethnicity, measures of disease severity, comorbid illnesses, baseline pulmonary function (percentage of predicted FVC and DL_{CO}) and screening biomarker levels (periostin and CXCL13) will be summarized for all randomized patients by treatment arm with use of descriptive statistics. Continuous variables will be summarized with the number, mean, median, standard deviation, minimum, and maximum. Categorical variables will be summarized with patient counts and percentages. Baseline data will be defined as the last observation before randomization.

4.4 EFFICACY ANALYSIS

All efficacy analyses will be performed on the Randomized Population. Unless otherwise specified, data collected during the 52-week placebo-controlled period will be used, regardless of whether the patient remained on treatment or discontinued the study drug early (but remained in the study). Analyses will be performed for Cohort A and Cohort B separately. For hypothesis testing, each cohort will be considered as a separate study and no type I error control will be done across the two cohorts.

For change-from-baseline endpoints, the baseline value will be defined as the measurement at randomization (Visit 2). If the randomization value is not available, the screening (Visit 1) value can be used in its place (last measurement prior to Day 1). For each subject, relative and absolute changes from baseline will be defined as follows:

- Absolute change from baseline = (post-baseline value – baseline value)
- Relative (%) change from baseline = $100 * (\text{post-baseline value} - \text{baseline value}) / (\text{baseline value})$

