4.1.2 Exclusion Criteria

Patients who meet any of the following criteria will be excluded from study entry:

- History of a severe allergic reaction or anaphylactic reaction to a biologic agent or known hypersensitivity to any component of the lebrikizumab injection
- Evidence of other known causes of ILD (e.g., domestic and occupational environmental exposures, connective-tissue disease [CTD], and drug toxicity)
- Lung transplant expected within 12 months of screening
- Evidence of clinically significant lung disease other than IPF (e.g., asthma or COPD)
- Post-bronchodilator forced expiratory volume in 1 second (FEV₁)/FVC ratio < 0.7 at screening
- Positive bronchodilator response evidenced by an increase of $\geq 12\%$ predicted and 200 mL increase in either FEV₁ or FVC

- Any clinically significant medical disease (other than IPF) that is associated with an expected survival of < 12 months, likely to require a change in therapy during the study, or likely to impact the ability of the patient to participate in the study in the opinion of the investigator, or impact the study efficacy or safety assessments
- Requirement for continuous medical care and assistance or limited ability to self-care that would impact the ability of patient to participate in the study or to perform the study-related assessments
- Class IV New York Heart Association chronic heart failure or historical evidence of left ventricular ejection fraction < 35%
- Hospitalization due to an exacerbation of IPF within 4 weeks prior to or during screening
- Known current malignancy or current evaluation for a potential malignancy
- Major episode of infection requiring any of the following:
 - Admission to the hospital for ≥ 24 hours within 4 weeks prior to screening or during screening and run-in period
 - Treatment with antibiotics (IV, IM, oral, or inhaled) within 4 weeks prior to screening or during screening and run-in period
- An active upper or lower respiratory tract infection occurring at any time within the screening period prior to the randomization visit (Visit 1 to Day 1, Visit 2)
- *Listeria monocytogenes* infection or active parasitic infection within 6 months prior to Day 1, Visit 2
- Active tuberculosis requiring treatment within 12 months prior to screening
- Known immunodeficiency, including but not limited to HIV infection
- Past use of any anti-IL-13 or anti-IL-4/IL-13 therapy, including lebrikizumab

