4.5.17.3 Assessments at Study Completion/Early Termination Visit

The study completion visit occurs as part of the last Safety Follow-up Visit (see [Appendix 1](#), [Appendix 2](#), and [Appendix 3](#)). All patients will be monitored for safety for 18 weeks after receipt of the final dose of lebrikizumab or placebo study treatment.

Patients who choose to prematurely discontinue study drug will be encouraged to remain in the study and complete all remaining assessments. If this is not feasible, the patient should enter and complete the safety follow-up period unless consent has been withdrawn.

Patients who withdraw from the study (regardless of the reason) and refuse safety follow-up will be asked to return to the clinic within 30 days (± 7 days) after the last dose of study treatment for an early termination visit. Refer to [Appendix 1](#), [Appendix 2](#), and

[Appendix 3](#) for the schedules of assessments performed at the study completion or early termination visit.

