2.2.3 Exploratory Efficacy Outcome Measures

The exploratory outcome measures for this study are as follows:

- Change from baseline to Week 52 in radiographic findings on pulmonary high-resolution computed tomography (HRCT), including quantitative lung fibrosis (QLF) score (see protocol)
- Change from screening (corresponding to timing for randomization strata) in serum and plasma biomarkers (e.g., periostin and CCL18) and change from baseline in serum and plasma biomarkers (e.g., periostin, CCL18, YKL40, COMP, OPN, CCL13)
- Serum lebrikizumab concentrations during the extended treatment and the 14-week safety follow-up period
- Exposure-response relationships (to be evaluated as warranted)
- Change from baseline to Week 52 in the Borg CR10 Scale
- Change from baseline to Week 52 in the ATAQ-IPF

- Time from randomization to first occurrence of SGRQ individual domain worsening as defined by reaching MID ([Swigris et al. 2010](#)).
 - Symptom=8
 - Activity=5
 - Impact=7
 - or death from any cause
- Change from baseline to Week 52 in the SGRQ
- Annualized rate of decrease in oxygen saturation levels (SpO₂) (%) over 52 weeks

The analysis plan for the exploratory HRCT and biomarkers will be specified in a separate document.

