4.4.2 Primary Efficacy Endpoint

The primary endpoint is annualized rate of decrease in percentage of predicted FVC through Week 52, which will be compared across treatment arms with use of a random slope model on observed cases at a 0.05 two-sided significance level.

The statistical model is as follows:

$$FVC_{ijk} = (\beta_0 + \beta_{0k}) + (\alpha_i * \beta_1 + \beta_{1k}) * t_k + \eta_k + \epsilon_{ijk}$$

where FVC_{ijk} is the predicted FVC for kth patient at visit j in treatment group i; β_0 is the intercept; α_i and β_1 is the interaction term of the treatment effect ($i = \text{lebri or placebo}$) and the slope; t_k is assessment time (continuous in year) for patient k; η_k is the effect of baseline lung function (defined as $FVC < 50\%$ vs. 50% to 75% vs. $> 75\%$ predicted) for the kth patient; β_{0k} and β_{1k} are the random components for intercept and slope; ϵ_{ijk} is the random error for kth patient at time j; β_{0k} , β_{1k} , and ϵ_{ijk} are assumed to be independent and normally distributed with mean 0 and variance of σ_0^2 , σ_1^2 , and σ_ϵ^2 respectively.

Of note, because of a relatively large number of strata defined by the randomization stratification factors, the analysis will be adjusted for baseline lung function only because baseline FVC may impact the clinical disease course.

From the model, least squares means for the annualized rate of decrease in each treatment arm and the difference between the two treatment arms will be provided with

95% CIs. The model implicitly imputes missing data based on an individual's estimated rate of worsening of lung function prior to study visit discontinuation (i.e., assuming missing at random).

There are several different approaches to summarizing the treatment effect which are ways of understanding the results rather than independent endpoints. For summarizing treatment effect the following will be provided but not considered as separate endpoints or hypotheses.

- Change from baseline to landmark visit time expressed as absolute and relative difference
- Difference in annual rate of decrease expressed as absolute and relative difference
- Categorical absolute change from baseline to each visit time with categories of decrease of $\geq 10\%$ or death before the visit, decrease of 10% to $>0\%$, stability or improvement of change $\geq 0\%$

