For time to first occurrence of a $\geq 10\%$ absolute decrease in percentage of predicted FVC or death from any cause, time to PFS, time to first occurrence of a $\geq 15\%$ decrease in percentage of predicted DL_{CO} or death from any cause, and time to first SGRQ Total Score ≥ 7 or death from any cause, deaths which occur within 168 days after the last clinic assessment and before the week 52 visit (and before start of open label treatment) will be counted as events. For the PFS analysis, hospitalization will be counted as events following the same rule as for death. Patients without an event will be censored at the last clinic assessment during the placebo controlled period. Any patients who undergo lung transplantation will be censored at the date of the transplant. Sensitivity analyses will be provided with lung transplant counted as an event for PFS and time from randomization to death or non-elective hospitalization from any cause. For the sensitivity analyses, only lung transplant, death, or non-elective hospitalization which occur within 168 days after the last clinic assessment and before the week 52 visit (and before start of open label treatment) will be counted as events.

Annualized Rate of Decrease Endpoints

The annualized rate of decrease in FVC (mL/year) will be analyzed and summarized with use of the same method as for the annualized rate of decrease in percentage of predicted FVC. Diffusing capacity, 6MWT distance, and the ATAQ-IPF score will also be analyzed and summarized with the same methods. For the annualized rate of decrease in FVC (mL/year) height, sex, and age will be included in the model as covariates.

Categorical summaries will be provided with categories of decrease of ≥ 50 meters or death before the visit, decrease of 50 to >0 meters, and stability or improvement of ≥ 0 meters for the 6MWT distance; summaries will be provided with categories of decrease of $> 15\%$ or death before visit, decrease of 15% to $>0\%$, stability or improvement of $\geq 0\%$ for percentage of predicted DL_{CO}.

Rules for missing ATAQ-IPF V3 and SGRQ data are described in Section 4.8.

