4.4.5 Sensitivity Analyses

The following additional sensitivity analyses will be performed:

- A. A Rank ANCOVA analysis of change from baseline to week 52 in percentage of predicted FVC stratified by baseline lung function (FVC < 50% vs. 50% to 75% vs. > 75% predicted) will be performed with death ranked as worst according to time until death (patient with the shortest survival time will be assigned the worst rank) and other missing results imputed the last observation carried forward method. These analyses will be performed as described in [Stokes et al. 2000](#).
- B. The annualized rate of decrease in *percentage of* predicted FVC over 52 weeks and the annualized rate of decrease in percentage of predicted DL_{CO} over 52 weeks will be performed using the random slope model with missing due to death imputed with the worst value observed in the study during the randomized treatment period, through week 52, among any Cohort A patient. Other missing data will be implicitly imputed by the model based on an individual's estimated rate of worsening of lung function prior to study visit discontinuation (i.e., assuming missing at random).
- C. The annualized rate of *decrease in percentage of* predicted FVC over 52 weeks will be performed using the random slope model with missing data imputed with the multiple imputation method only from placebo patients. The multiple imputation method will be implemented with the following specifications.
 1. 100 imputation datasets will be created separately from steps a and b
 - a) The MCMC method will be used for partial imputation of non-monotone missingness, only to produce a monotone missing pattern. The seed will be 5815733.
 - b) The monotone method will then be used with regression method. The baseline lung function (FVC < 50% vs. 50% to 75% vs. > 75% predicted), treatment group, and all prior visits will be included in the model to impute the following visit. The seed will be 8246205

2. The random slope analysis will be performed for each imputation dataset and the results will be combined following the methodology developed by Rubin (1978, 1987).

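### The slope and MMRM analyses have no lung-transplant rule, so lung function measured after an unexpected transplant can count as improvement on the primary endpoint

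*Combined protocol and SAP*

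**What the plan says.** SAP 4.4 sets the data rule for all efficacy analyses. Unless a section specifies otherwise, "data collected during the 52-week placebo-controlled period will be used, regardless of whether the patient remained on treatment or discontinued the study drug early", provided the patient stayed in the study. SAP 4.4.2 compares the arms on annualized decrease in percent predicted FVC with a "random slope model on observed cases at a 0.05 two-sided significance level". The same section adds an MMRM of change from baseline to Week 52.

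SAP 4.4.3 extends the slope method to FVC in mL/year, and "Diffusing capacity, 6MWT distance, and the ATAQ-IPF score will also be analyzed and summarized with the same methods". SAP 4.4.4 applies it to SpO2, which SAP 2.2.3 lists as exploratory: "Annualized rate of decrease in oxygen saturation levels".

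Transplant appears in the analysis text only for time-to-event endpoints. SAP 4.4.3 says: "Any patients who undergo lung transplantation will be censored at the date of the transplant". It adds a sensitivity analysis counting transplant as an event for PFS and for death or non-elective hospitalization. Protocol 6.4.2 has the same rule for time-to-event endpoints in general.

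Two protocol provisions bear on how often post-transplant values could arise. Section 4.1.2 excludes patients with "Lung transplant expected within 12 months of screening". Section 4.5.17.3 says: "Patients who choose to prematurely discontinue study drug will be encouraged to remain in the study and complete all remaining assessments".

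**The concern.** After a lung transplant, FVC and DLCO no longer describe the course of IPF in the patient's own lungs. A patient ill enough to be transplanted may have had one of the worst courses in the trial, yet higher values afterwards would give that patient one of the best fitted slopes. The time-to-event rule shows that transplant was foreseen, but nothing equivalent was written for the primary endpoint. That endpoint gates the whole fixed testing sequence in SAP 4.4.1, where the DLCO, ATAQ-IPF and 6MWT slopes also appear. An excess of transplants on placebo would hide a benefit of lebrikizumab; an excess on lebrikizumab would inflate one.

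**Working it through.** **1. Is there a rule elsewhere?** The primary model and MMRM (SAP 4.4.2), the other slopes (4.4.3, 4.4.4), sensitivity analyses A to D (4.4.5) and the missing-data section (4.8) do not mention transplant. The default in 4.4 therefore applies. The sensitivity analyses compare as follows:

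- A (rank ANCOVA) ranks deaths worst. An observed Week 52 value after transplant is ranked as it stands.
- B is the "random slope model with missing due to death imputed with the worst value observed in the study during the randomized treatment period", and D is the MMRM counterpart. Both act only on values missing because of death.
- C imputes missing values only. Post-transplant values are observed.

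**2. The plan's own power.** Inputs from SAP 2.3: SD 8, two-sided alpha 0.05, 75 per arm and 3.7 points/year (Cohort A), 165 per arm and 2.5 points/year (Cohort B). SE = 8 × √(2/n); power ≈ Φ(difference/SE − 1.96).

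- A: SE = 1.306; 3.7/1.306 − 1.96 = 0.872; power 0.81.
- B: SE = 0.881; 2.5/0.881 − 1.96 = 0.878; power 0.81.

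Both agree with the stated figure of about 80%.

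**3. One patient's slope.** Spirometry is at Weeks 0, 1, 4, 12, 24, 36, 44 and 52. The mean is 173/8 = 21.625 and Sxx = 6673 − 173²/8 = 2931.9. Assume a transplant at Week 30 and a step of J points at Weeks 36, 44 and 52. The fitted slope changes by J × (132 − 3 × 21.625)/2931.9 × 52 = 1.19 × J per year. For J = 10, 20 and 30 that is +11.9, +23.8 and +35.7 points/year. With the planned Cohort B control slope of −4.1, a 20-point step gives −4.1 + 23.8 = +19.7.

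**4. The arm difference.** With all patients on the same visits, the contrast moves by roughly the patient's slope change divided by n. A generalized least squares calculation for the SAP model (assumed SDs: intercept 12, slope 7, residual 3) gives the same values. The table shows one transplant in one arm and none in the other.

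| Step J (Week 30) | Cohort B, n = 165 | % of 2.5 | Cohort A, n = 75 | % of 3.7 |
|---|---|---|---|---|
| 10 | 0.07 | 3% | 0.16 | 4% |
| 20 | 0.14 | 6% | 0.32 | 9% |
| 30 | 0.22 | 9% | 0.48 | 13% |

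Slope SD 6 with residual SD 4 gives nearly the same shifts.

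**5. A harsher scenario.** Assume a decline of 15 points/year, a transplant at Week 20, and FVC then 15, 25 or 35 points above baseline. The patient has lost 15 × 20/52 = 5.8 points by then, so the step is about 21, 31 or 41 points. Fitting Cohort B with and without the post-transplant values gives shifts of 0.16, 0.23 and 0.30 points/year, the last being 0.30/2.5 = 12% of target.

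**6. More than one transplant.** With two on placebo and none on lebrikizumab in Cohort B at Week 30, the shift is 0.14, 0.29 or 0.43 and power falls from 0.81 to 0.76, 0.71 or 0.65. With two in each arm the shift is 0. These powers hold the SD at 8; outlying slopes would also raise the variance.

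**The case against.** The strongest case against is that this will rarely matter. Patients expected to be transplanted within 12 months of screening are excluded, which nearly covers the 52-week window. Attendance after stopping drug is encouraged but not assured, and SAP 4.4 covers only patients who remain in the study. In Cohort B one transplant moves the estimate by 0.07/0.88 = 0.08 to 0.30/0.88 = 0.34 standard errors, and balanced transplants cancel. The rank analysis limits any single outlier's influence, and using all observed data in randomized patients is a recognised strategy. All of this stands, and it keeps the point small. It does not supply the missing rule, and even under the rank analysis such a patient would still rank favourably.

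Four stronger readings do not hold:

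- A reader might infer that post-transplant values will enter as large improvements, or that the primary result will be biased. The documents contain no transplant counts, no post-transplant measurements and no reason to expect imbalance between arms.
- A reader might count SpO2 among the affected primary or secondary slopes. It is exploratory and outside the testing sequence.
- A reader might take the censoring rule as the SAP's admission that post-transplant data are invalid. The SAP gives no rationale for censoring.
- A reader might want Cohort A corrected prospectively. Protocol 1.4 and SAP 2.4 show that it was unblinded in May 2016 and analysed.

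**Conclusion.** The gap is real. The data rule in SAP 4.4 keeps post-transplant values in the primary FVC slope, the MMRM and the DLCO, 6MWT, ATAQ-IPF and SpO2 slopes. No planned analysis removes or offsets them. Whether this matters depends on an unexpected transplant occurring, the patient being measured afterwards, and the arms differing in number. On assumed steps and timing, the size in Cohort B is about 0.07 to 0.3 points/year per unmatched transplant. This is a cheap improvement to the plan. It is not evidence that either cohort's result is wrong.

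**What to change.** Before Cohort B is unblinded, add to SAP 4.4: *FVC and DLCO values obtained on or after the date of lung transplant are excluded from all slope and change-from-baseline analyses; the same applies, for consistency, to the other slope endpoints.* The case is strongest for lung function. Extending it to walk distance, ATAQ-IPF and SpO2 is more a matter of choosing the estimand.

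In sensitivity analyses B and D, handle transplant as death is handled there. This is needed because, after the exclusion, the primary model treats post-transplant time as missing at random, which may be optimistic for a patient who needed a transplant.

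The cost is two sentences and one data-handling flag; the transplant date is already required by the time-to-event rule. A few observations are lost. For Cohort A, the same exclusion can be reported only as a post hoc sensitivity analysis, labelled as such.
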